2.10.4 PATIENTS REPORTING INTOLERABLE SYMPTOMS

The GP will remain as the first point of contact for patients during the trial for their care. Intolerable muscle symptoms should be reported to the GP who will provide clinical care as directed by the appropriate NICE guidelines. Where a patient reports intolerable symptoms, Figure 2 shows the decision making pathway for the GP and the patient.

For patients who experienced intolerable muscle symptoms, and who do not want to be withdrawn early from the trial, the GP will be asked to confirm that the patient still meets the trial eligibility criteria. Patients who continue to meet the eligibility criteria can be offered the following options by the GP, depending on their clinical judgement:

- i. continue with their current treatment
- ii. reduce the frequency of tablet use to every other day rather than daily
- iii. stop for that treatment period and resume at the start of the next period

[figure not shown]

Figure 2: Intolerable symptoms pathway

Patients who withdraw from treatment temporarily or permanently will be asked to inform the study team and report symptoms at the time of stopping, and continue to submit outcome data for their current treatment period.

2.10.5 EARLY WITHDRAWAL OF PATIENTS FROM THE TRIAL

A patient is free to change their minds about participation at any time. We would advise that the patient see their GP to discuss future routine care. A GP can withdraw a patient at any time if clinical

concerns arise or if the patient presents with any reason to stop atorvastatin as described in the Summary of Product Characteristics for Atorvastatin 20 mg (Appendix 8). In each case, an end of trial form (Appendix 3) should be completed.

2.11 ADVERSE EVENTS

Reporting of Adverse Events for this trial: Atorvastatin is not a new drug and has a well-documented safety profile. Furthermore, this trial is being conducted in a population in which statin use is clinically indicated. It is anticipated that patients in this trial are at higher risk of cardiovascular diseases because of underlying clinical conditions requiring statin use. Additionally, as participation is for 15 months it is likely that they will have common medical problems (e.g. colds, coughs, fevers etc). On the basis that patients: (1) would have had prior exposure to the trial treatment, (2) the trial treatment is clinically indicated for their medical condition, and (3) the known safety profile of the trial treatment, we will limit adverse events to be reported to those events that fulfill the Serious Adverse Event (SAE) criteria as described below.

Patient Self-report: In the two-monthly questionnaire, patients will be asked to self-report any event which resulted in unplanned hospital admissions. Where a patient indicates that there was an unplanned admission, the GP/Research Nurse will be asked to submit a brief report to the CTU.

General Practitioner report: Participating GPs will report any event to the CTU that fulfill the Serious Adverse Event (SAE) criteria as described below within 24 hours of becoming aware of the event. To minimize the risk of unreported events, at two-monthly intervals, the Research Nurse/GP will conduct a search of their database for any StatinWISE patients who have been recorded as having died.

Definitions:

Adverse Event (AE): Any untoward medical occurrence not listed in the Investigational Medicinal Product Dossier (IMPD) and /or Summary of Product Characteristics (SmPC) affecting a trial participant during the course of a clinical trial.

Serious Adverse Event (SAE): A serious adverse event (experience) is an adverse event (as defined above) which at any dose:

- results in death
- is life-threatening
- requires inpatient hospitalisation or prolongation of existing hospitalisation; or
- results in persistent or significant disability/incapacity
- is a congenital anomaly/birth defect

Adverse Reaction (AR): An AE when there is at least a possibility that it is causally linked to a trial drug or intervention.

Serious Adverse Reaction (SAR): SAE that is thought to be causally linked to a trial drug or intervention.

Suspected Unexpected Serious Adverse Reaction (SUSAR): An *unexpected* occurrence of a SAR that is inconsistent with the list of expected events in the Summary of Product Characteristics for atorvastatin 20 mg dated 02/09/2015 (Appendix 8); there need only be an index of suspicion that the event is a previously unreported reaction to a trial drug or a previously reported but exaggerated or unexpectedly frequent adverse drug reaction.

All SAEs assigned by the PI or delegate as both suspected to be related to IMP-treatment and unexpected will be classified as SUSARs and will be subject to expedited reporting to the Medicines and Healthcare Products Regulatory Agency (MHRA). The Sponsor (or delegate) will inform the MHRA, and the ethics committee of UK-relevant SUSARs within the required expedited reporting timescales (no later than 7 days after the Sponsor was first made aware for fatal/life threatening reactions; no later than 15 days for other reactions).

As this is a blinded trial, all SUSARs must be reported to the Sponsor (or delegate) assuming the active compound is involved. All expedited reports submitted to the regulatory authorities will be unblinded.

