2.4 SAMPLE SIZE

A sample size of 64 participants provides approximately 90% power to detect a treatment effect of at least 10mm, assuming a Type I error of 5%. Allowing for loss to follow-up of 40% of participants through the trial inflates the required sample size to 107 participants.

Period effects (changes in underlying VAS pain score due to factors other than randomised treatment, e.g. seasonal, activity-related, etc.), variability in individual statin effects across patients, and imperfect adherence to the assigned treatment were investigated by further detailed simulations. VAS pain scores are not normally distributed, since they are bounded (0-100mm) and can display large fluctuations in response. Therefore, further power calculations were performed drawing the outcome from a Beta distribution, and from a distribution with normal variance components on a logit scale, to assess the robustness of the sample size estimates to the distribution chosen. These factors all have the effect of decreasing power, thus increasing the sample size required. An approximate 80% increase in the sample size required in the absence of these effects provided approximately 90% or more power across a plausible range of these potential effects, thus we determined that a final sample size of 200 was required.

Multiple testing: Rather than making formal adjustments for multiple testing, we follow an approach advocated by Pocock²⁵ of clearly specifying our primary analysis (which provides a single test for treatment effect), while explicitly presenting and interpreting all other tests as secondary analyses.

Power for individual N-of-1 trials: In order to increase the statistical power for the analysis of individual N-of-1 trials, we will ask participants to report symptoms daily in the last week of each period, rather than once per period. Full adherence through the trial will provide between 55 and 70% power to detect effects of 10mm or greater for individual treatment comparisons.

Estimates of recruitment and retention rates: We anticipate that some patients will not complete data in each treatment period, and that some will not complete their 12-month follow-up. By designing this study as a series of N-of-1 trials, which offer individual participant benefit in the form of an individualised estimate of effect, we hope to minimise this type of dropout. However, we have accounted for this in our sample size calculation by allowing for 40% loss to follow-up.

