2.16 END OF TRIAL FOR PARTICIPANTS

The follow-up period ends 15 months after the first treatment day with a final contact (telephone or face-to-face) with the Research Nurse as described above. This will be considered as the end of trial for patients.

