[figure not shown]
4. *(appears if the participant ticks yes for Question 1):* Indicate with a cross (x) on the scale the number that describes how, during the last two months, pain has interfered with your:

- General activity
- Mood
- Walking ability
- Normal work (includes both work outside the home and housework)
- Relations with other people
- Sleep
- Enjoyment of life

For each of (a) to (g), the following scale will appear:

5. (appears if the participant ticks yes for Question 1): **On the diagram, tap to highlight the area that hurts the most.**
(Paper form will read: 'On the diagram, put an X on the area that hurts the most.')

More than one area

The body will be divided into the following locations and answers should be categorized depending where the participant taps. For paper forms, the location given by X marked on the body will be entered into the web or app version at data entry. Locations: head and neck/upper limbs/lower limbs/trunk.

6. (All participants): **In the last two months, have you experienced any other symptom that you think is associated with your study medication?**

Yes (please specify)
(free text)
 No
 Don't know

PART 3: ADVERSE EVENTS

1. (All participants): **Have you been admitted to hospital in the last two months?**

Yes
 No

[figure not shown]
[figure not shown]
2. (Appears if the participant ticks yes for Question 1): **What was the reason for your admission to hospital?**

[figure not shown]
[figure not shown]
[figure not shown]
[figure not shown]
(free text)

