In the two-monthly questionnaire, patients will be asked to self-report any event which resulted in unplanned hospital admissions. Where a patient indicates that there was an unplanned admission, the GP/Research Nurse will be asked to submit a brief report to the Trial Coordinating Team and where the event is believed to be unexpected and associated with statin use, an Adverse Event Report Form will be completed. Participating GPs will also report any event to the trial team which results in unplanned hospital admissions, patient death or where a patient has a baby with any congenital anomaly/birth defect within 24 hours of becoming aware of the event. To minimize the risk of unreported events, at two-monthly intervals, the Research Nurse/GP will conduct a search of their database for any StatinWISE patients who have been recorded as having died. The GP/Research Nurse will be asked to submit a brief report to the Trial Coordinating Team and where the event is believed to be unexpected and associated with statin use, an Adverse Event Report Form will be completed

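### Capture of unplanned hospital admissions has avoidable gaps: the record search looks only for deaths, and the questionnaire's fixed two-month recall cannot recover a missed form

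*Protocol*

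**What the plan says.** Protocol 2.11 limits safety reporting to serious adverse events and counts inpatient hospitalisation among the criteria. It sets out three routes to the CTU.

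- **Patient.** "In the two-monthly questionnaire, patients will be asked to self-report any event which resulted in unplanned hospital admissions". Appendix 4 has the form completed on day 56 of each period, and its Part 3 asks: "Have you been admitted to hospital in the last two months".
- **GP.** The practice reports a qualifying event within 24 hours of learning of it. SAP 1.2 names unplanned admissions alongside deaths and congenital anomalies.
- **Record search.** SAP 1.2 gives both the purpose and the interval: "To minimize the risk of unreported events, at two-monthly intervals, the Research Nurse/GP will conduct a search of their database". In both documents the target is deaths only; the protocol's wording is "the Research Nurse/GP will conduct a search of their database for any StatinWISE patients who have been recorded as having died".

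Four other places determine how much time the patient route covers. Protocol 2.9.3 allows breaks between periods. Section 2.10.4 asks patients who stop treatment, temporarily or permanently, to "continue to submit outcome data for their current treatment period". Section 2.16 states: "The follow-up period ends 15 months after the first treatment day". The End of Trial/Early Withdrawal form (Appendix 3) and the month-15 contact (Protocol 2.10.3, SAP 1.2) record the statin decision and whether the result helped; neither has an admission item.

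SAP 2.3.3 tabulates serious adverse events by allocated treatment, and SAP 1.11 gives the DMC oversight of safety.

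**The concern.** The plan accepts that reporting by GPs and patients can miss events and adds an active check for that reason, but the check protects one category only. Protocol 2.11 itself expects these patients to be at raised cardiovascular risk, so admissions are foreseeable.

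The patient route does not close the gap. Each form looks back a fixed two months, so if one form is never returned, the next does not ask about the lost period. For a patient who stops for good, no later form is specified. The form completed at withdrawal does not ask about admissions at the moment self-report ends.

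What is at stake is the completeness of the serious adverse event tables and of what the DMC sees. The item also does not ask for an admission date, so even a reported admission may be hard to place in the right treatment period.

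**Working it through.** **The plan's own figure.** Protocol 2.4 inflates 64 participants to 107: "Allowing for loss to follow-up of 40% of participants through the trial". Check: 64 / (1 − 0.40) = 106.7, which rounds up to 107 and reproduces. Applied to the 200 patients to be recruited, the same allowance is 200 × 0.40 = 80 patients. Planned questionnaires: 200 × 6 = 1,200. The documents give no admission rate and no figure for capture.

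**Which route covers which window.**

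| Window | Patient form | Record search | GP report |
|---|---|---|---|
| Period with form returned | yes | deaths only | yes |
| Period with form never returned | no; next form looks back two months only | deaths only | yes |
| Longer break before a period | no | deaths only | yes |
| After permanent stopping, later periods | none specified | deaths only | yes |
| After period 6, to month 15 | no admission item on any form | deaths only | yes |

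On breaks: two months is about 2 × 30.4 = 61 days and the form falls on day 56, so recall reaches back about 5 days before the period starts. A longer break is partly uncovered.

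**Periods without self-report.** Assume the 80 losses are spread evenly over the six periods and that no later form is sent.

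- Withdrawal-period form sent, as 2.10.4 requests: mean periods lost (5+4+3+2+1+0)/6 = 2.5; 80 × 2.5 = 200; 200/1,200 = 16.7%. Range: 0 (all lost in period 6) to 80 × 5 = 400 (33%, all lost in period 1).
- Withdrawal-period form not sent: mean (6+5+4+3+2+1)/6 = 3.5; 80 × 3.5 = 280; 280/1,200 = 23.3%. Range: 80 (7%) to 480 (40%).

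A constant withdrawal hazard instead of an even spread gives nearly the same answer. With 1 − (1 − h)^6 = 0.40, h = 0.082. Self-report then covers 82% of periods if the withdrawal-period form is sent and 75% if not, leaving 18% to 25%.

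**Could the loss differ by treatment?** For each of the eight sequences in Protocol 2.8, take the probability of still being in the trial at the start of each period. Multiply it by 1 if the withdrawal-period form is sent, or by (1 − hazard in that period) if it is not. Average over statin and placebo periods separately, with hazards scaled so that 40% withdraw overall.

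| Assumed withdrawal hazard ratio, statin:placebo | Difference in coverage (percentage points) |
|---|---|
| 1 | 0 |
| 1.5 | 1.4 |
| 2 | 2.3 |
| 3 | 3.4 |

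Statin has the lower coverage if the withdrawal-period form is missed; placebo has it if that form is sent. These figures concern self-report only, before any GP report.

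**After treatment.** In nominal months the uncovered time is 3/15 = 20% of participation. With periods of exactly 56 days (SAP 2.3.1), 6 × 56 = 336 days; 15 months is about 457 days, so about 120 days (26%) have no form with an admission question.

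**The case against.** The strongest reply is that limited safety reporting is a reasoned choice in a low-risk setting with a long-marketed drug, and that other safeguards exist. Forms are prompted and chased (Protocol 2.10.2), and staff can complete them by telephone (2.10). The record carries a participation code and the patient an alert card (2.10.3). The GP is the first point of contact, and the investigator must report events promptly (3.6). All of this stands and reduces the gap. None of it asks about an admission in a window that no form covers.

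Appendix 1 also appears to mark adverse event reporting in the follow-up column, and a nurse contact in month 14 and a staff contact in month 15 are planned. The mark is weak evidence, since the daily-medication row carries the same one. If it is intended, no form implements it, and the passages should be reconciled.

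A reader might infer more than the documents support, in three ways.

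- *That admissions in months 13–15 are lost unequally by treatment.* Those months follow all six randomised periods. Every completer has by then been allocated three periods of each treatment, and no treatment is allocated. That is under-capture, not a biased comparison.
- *That everyone who stops treatment leaves the form cycle.* Section 2.10.4 also covers temporary stopping, with a return at the next period.
- *That serious events are shown to be selectively under-counted on one treatment.* SAP 2.3.7 will explore whether withdrawal differs by treatment, and intolerable muscle symptoms are a listed withdrawal reason, so dependence is plausible. The documents do not show it; the calculated difference is small and its direction is not fixed.

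Two further limits stand. The documents do not show how readily unplanned admissions can be retrieved from practice records. Nor do they settle record access after withdrawal: SAP 1.12 covers data collected up to withdrawal of consent.

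**Conclusion.** Capture of unplanned admissions is incomplete by design, and a cheap change would improve it. Under the 40% allowance, roughly 17% to 23% of planned treatment periods would have no self-report. This rests on an even spread of losses and on no forms after withdrawal; the timing extremes run from 0% to 40%. The figure counts periods resting on GP reporting alone. It does not estimate missed admissions, which the documents do not allow.

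Unequal loss by treatment can arise only within the six treatment periods and is not demonstrated. The time from the end of period 6 to month 15 is a matter of completeness only. The primary VAS analysis, sample size and power are unaffected. This is a worthwhile improvement to safety data, not a defect that threatens the trial's main conclusion.

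**What to change.** 1. In Appendix 4, Part 3, Q1, replace the two-month window with *since your last completed questionnaire (or since starting, if none)*, and ask for the date of admission so that the event is assigned to the right period.
2. Add the same item to the End of Trial/Early Withdrawal form (Appendix 3) and to the month-15 contact, and reconcile Appendix 1 with the forms.
3. In Protocol 2.11 and SAP 1.2, extend the two-monthly search to recorded unplanned hospital admissions, for all randomised patients to month 15, including those off treatment, where consent to record access continues.

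Cost: somewhat more search effort and a few more brief reports per practice. Before the third change is adopted, confirm with practices that admissions can be found by such a search. The first two do not depend on it. No change to sample size, significance level or power is needed.

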2.14 MONITORING

GCP section 5.18.3 states in regard to monitoring, *"The determination of the extent and nature of monitoring should be based on considerations such as the objective, purpose, design, complexity, blinding, size and endpoints of the trial. In general, there is a need for on-site monitoring, before, during, and after the trial; however, in exceptional circumstances the sponsor may determine that central monitoring in conjunction with procedures such as investigators training and meetings, and extensive written guidance can assure appropriate conduct of the trial in accordance with GCP. Statistically controlled sampling may be an acceptable method for selecting the data to be verified."*

StatinWISE is a pragmatic, randomised placebo controlled trial. The intervention (atorvastatin) has marketing authorisation in the United Kingdom and has been in clinical use for decades. The trial will collect data on SAEs which may be associated with this product and other clinical conditions which will be common in this population. These events will be reviewed routinely by the trial Medical Advisor and will be reported routinely to the Trial Steering Committee. The trial involves getting consent, giving the trial drug in the usual way and collecting information regarding muscle symptoms directly from the patients. There are no extra tests or procedures unless patients agree

to take part in the genetic study, for which 9 ml of blood is required. Apart from the trial drug, any other medication will be issued as per usual practice under the care of the GP. For these reasons, we believe that the risk of harm or injury (whether physical, psychological, social or economic) to trial patients is low. We will use central monitoring along with investigators' training and meetings, and extensive written guidance to make sure the trial is carried out properly. Statistically controlled sampling will be used to select data to be verified at GP practices. We plan to carry out on-site monitoring where central statistical monitoring show abnormality. Consent forms will be monitored centrally at the CTU.

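### Protocol 2.11 restricts adverse events to unlisted ones, which contradicts its own expectedness test and leaves the SAE status of listed serious events open to interpretation

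*Protocol*

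**What the plan says.** The definitions are in Protocol 2.11.

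- An adverse event is "Any untoward medical occurrence not listed in the Investigational Medicinal Product Dossier" and/or the Summary of Product Characteristics.
- For seriousness: "A serious adverse event (experience) is an adverse event (as defined above) which at any dose" meets one of five criteria (death, threat to life, hospitalisation, disability, birth defect).
- An adverse reaction is an AE with a possible causal link. A SAR is an SAE thought to be causally linked.

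Reporting is restricted by seriousness: "we will limit adverse events to be reported to those events that fulfill the Serious Adverse Event (SAE) criteria as described below". For general practitioners the rule is that they "will report any event to the CTU that fulfill the Serious Adverse Event (SAE) criteria as described below within 24 hours of becoming aware".

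The SUSAR text in the same section then compares a SAR with the expected events in the dated SmPC. It also covers a "previously reported but exaggerated or unexpectedly frequent adverse drug reaction". The classification rule is: "All SAEs assigned by the PI or delegate as both suspected to be related to IMP-treatment and unexpected will be classified as SUSARs".

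Protocol 2.14 says of the SAEs collected: "These events will be reviewed routinely by the trial Medical Advisor and will be reported routinely to the Trial Steering Committee". The End of Trial form (Appendix 3, item B.6) requires an SAE form for any death. SAP 2.3.3 tabulates adverse events, SAEs and SUSARs by allocated treatment.

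**The concern.** Whether an event is listed in the reference document normally decides only whether a reaction is expected. Here it decides whether the event is an adverse event at all, and every later category inherits the restriction. The types removed are those already linked to atorvastatin.

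For a listed serious event, three things are then not assured: classification as an SAE, the Medical Advisor and Steering Committee review in Protocol 2.14, and entry in the SAE table in SAP 2.3.3. On the same reading the GP's 24-hour duty in Protocol 2.11 would not apply either. If practices read the text differently, the SAE table would reflect local interpretation as well as events.

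**Working it through.** No figure in the plan is at issue, so the check follows the definitions and compares them with the other safety text.

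**1. The chain.** If an AE must be unlisted, every SAE is unlisted because it is an AE as defined above, and every SAR is unlisted because it is an SAE. SmPC 4.8 (Protocol Appendix 8) lists rhabdomyolysis, pancreatitis and hepatic failure. A patient hospitalised with any of these would not have an SAE.

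**2. Against the SUSAR text.** The rule selects SAEs that are both related and unexpected, so it presupposes that some related SAEs are expected. Under step 1 there are none, and the test is redundant. For a listed reaction, the limb on unexpectedly frequent reactions cannot be reached. The limb on exaggerated ones can be reached only if the exaggerated form counts as unlisted.

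**3. Against the End of Trial form.** Item B.6 wants an SAE form for every death. A death from a listed cause would need an SAE form for something that step 1 says is not an SAE.

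**4. The reference documents differ.** The AE definition uses the IMPD and/or the SmPC. The SUSAR definition uses the SmPC alone.
- If listing in either document excludes an event, step 1 holds for everything in SmPC 4.8.
- If listing in both is needed, an SmPC-listed event that is absent from the IMPD remains an AE. The IMPD is not among the documents, so this cannot be settled.

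**5. Routes that do not depend on listing.**
- Unplanned admissions: patients report them, and then "Where a patient indicates that there was an unplanned admission, the GP/Research Nurse will be asked to submit a brief report to the CTU". Appendix 4 Part 3 asks about any admission and its reason.
- Deaths: the two-monthly database search (Protocol 2.11) and End of Trial form B.6.
- Admissions, deaths and birth defects: GP notice within 24 hours (SAP 1.2).
- Some other events: the End of Trial form completed at early withdrawal (Protocol 2.10.5; reasons in Appendix 3, B.3), and the Appendix 4 alert to the trial team when a doctor advises stopping because of muscle symptoms.

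Of these, only B.6 leads to an SAE form. The Adverse Event Report Form in SAP 1.2 is completed only if the event is thought both unexpected and associated with statin use. The documents do not say that the brief reports become SAE records.

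**6. Scale.** Rates are given only for two listed types (Protocol 1: rhabdomyolysis 0.1 and myopathy 0.5 per 1,000 people over 5 years).
- Statin exposure: 200 patients × 3 periods × 2 months = 1,200 months = 100 person-years.
- Rhabdomyolysis: 0.1 / 1,000 / 5 × 100 = 0.002 expected cases.
- Myopathy: 0.5 / 1,000 / 5 × 100 = 0.010 expected cases.
- If only 60% of the exposure is retained (assumption: the 40% loss in Protocol 2.4, taken as lost from the start): 0.0012 and 0.006.

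The total over all listed types cannot be derived, because the documents do not say what share of listed events is serious.

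**7. Effect of deleting the clause alone.** Myalgia and muscle spasms are listed in SmPC 4.8, and muscle symptoms are the primary outcome. Once listed events count as AEs, a symptom could be recorded as an AE on up to 200 × 6 = 1,200 questionnaires and 200 × 6 × 7 = 8,400 daily entries. Protocol 2.11 limits reporting to serious events, but SAP 1.9, 1.10 and 2.3.3 do not repeat that limit.

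**The case against.** A reader might infer that listed serious events would go unreported. The documents do not support this. Most listed admissions and all deaths reach the CTU by the routes in step 5, and SAP 1.2 gives 24-hour GP notice for unplanned admissions, deaths and birth defects without asking about listing.

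A reader might also infer that listed life-threatening or disabling events without admission or death have no route at all. That goes too far. Withdrawal forms and stopping alerts can bring some of them to light, although these routes are conditional and carry no 24-hour clock.

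The literal reading is also not the only one. The and/or wording may exclude less than it seems to. A GP may take the phrase *SAE criteria* to mean the five seriousness criteria alone and report listed events anyway. The SUSAR rule, the collection of product-associated SAEs in Protocol 2.14 and End of Trial form B.6 all suggest that listed serious events were meant to be captured. The SAE form and the operating manual are not among the documents and may settle the matter in practice.

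All of this limits the consequences, but the contradiction remains. The definition expressly refers back to the restricted AE. Protocol 2.11 justifies limiting reports by seriousness and gives no reason for leaving out listed serious events. Having several reasonable readings is itself the problem when practices classify events independently.

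**Conclusion.** The concern holds as a minor internal inconsistency. The AE definition in Protocol 2.11 cannot be reconciled, on its literal reading, with the SUSAR text in the same section or with End of Trial form B.6. What is at risk is consistent SAE classification, the review attached to it, and the completeness of a descriptive table.

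The primary estimate, power and type I error are unaffected. Expected rhabdomyolysis and myopathy counts are close to zero (0.002 and 0.010), on the assumption that the Introduction's rates apply to this population. The total number of listed serious events is unknown, so no claim is made about how many would be misclassified. The conclusion rests on the text supplied. The IMPD, the SAE form or the operating manual could narrow the practical effect, but the protocol wording would still need correcting.

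**What to change.** 1. **Protocol 2.11.** Delete the restriction to events not listed in the IMPD and/or SmPC from the AE definition. Keep expectedness only in the SUSAR definition.
2. **Keep the seriousness limit and carry it through.** Retain the rule that only events meeting a seriousness criterion are reported. Align the investigator's duty in Protocol 3.6 and the adverse event row in Appendix 1, both of which currently refer to adverse events without that limit. In SAP 1.9, 1.10 and 2.3.3, use a single SAE variable and table, plus SUSARs. Non-serious muscle symptoms are then not coded as AEs, and the AE and SAE tables do not duplicate each other.
3. **SAP 1.2.** State that every event meeting a Protocol 2.11 seriousness criterion is recorded as an SAE, whatever its expectedness or presumed cause.

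The cost is one deleted clause, two wording alignments in the protocol and a few SAP sentences. The downside is a few more SAE forms. Randomisation, outcome collection and the primary analysis do not change.
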